**Describe the background and rationale for this project:**

The commonly used method for endotracheal intubation in children is direct laryngoscopy using a Miller or Macintosh blade. Videolaryngoscopy is a widely accepted pediatric airway management. Videolaryngoscopes (VL) provide an indirect view of glottis without the need to align the oral, pharyngeal, and glottis structures. Some types of VLs provide also direct view of glottis with indirect view. Videolaryngoscopes can be used as a teaching tool for learners as they can visualize all the anatomical structures of larynx at the same time with the performer. VLs may facilitate the learning of endotracheal intubation in inexperienced users in the pediatric population. There are limited data on the use of videolaryngoscopes by anesthesia providers and medical personnel who are inexperienced in the use of videolaryngoscopes.

**How will your study be funded:** No funding is required for this study.

**Provide a potential start date and end date for your study to be included in the IRB application:** start date of 6/27/2016 – end date of 7/30/2016 (1 month period).

**List any sub-Investigators you want to participate as back-up/support on the study -** [name], [name], [name]

**Describe the significance of the proposed research:** To compare the CMAC and Glidescope videolaryngoscopes (VL) to traditional direct laryngoscopy (DL) using either a Miller or Macintosh laryngoscope by studying the performance of users. This will involve the use of an intubating pediatric manikin to

assess various aspects of endotracheal intubation by experienced and inexperienced users. The inexperienced users in intubation of children will use VLs on a pediatric manikin. We will evaluate the success rates of inexperienced and experienced users and compare their results. These results will help us to see if inexperienced users are successful with VLs. Also we will assess whether VLs are a good teaching tool and if they can be preferred as a first line tool for pediatric intubation.

**State the primary and secondary objectives of the study:** The goal of the study is to test whether time to intubation is shorter with VL as compared to DL. We hypothesize that this difference will be greatest for users with the least experience in DL. Secondary aims include comparing success rates and user-rated ease of intubation between VL and DL.

**If this research is hypothesis driven, succinctly state the hypothesis:** Performers who are inexperienced about direct laryngoscopy and VL will achieve higher overall success rates using videolaryngoscopes than using a direct laryngoscope.

**Outline the major steps and methodologies in the clinical protocol.** Direct laryngoscopy using a Miller and Macintosh laryngoscope as well as indirect laryngoscopy using a CMAC and Glidescope VL devices will be used. Each participant will perform endotracheal intubation on the mannequin using both types of laryngoscope blades and both types of indirect laryngoscopes (total of 4 intubation attempts each). In a given subgroup, a two-tailed paired t-test on a sample of 10 subjects would have 80% power to detect a 15s difference in time to intubation between videolaryngoscopy and direct laryngoscopy at a 95% confidence level, assuming mean time to intubation of  $45 \pm 15$  seconds with videolaryngoscopy and low within-subject correlation ( $r=0.5$ ) between times to intubation with the different methods in the study. Therefore, the study will recruit 10-20 personnel from each of the following 4 groups:

1. Faculty pediatric anesthesiologists
2. CRNAs
3. Trainees (SRNAs, residents, and fellows, and medical students)
4. APNs from the PICU/CTICU. Nurses at NCH

Time to endotracheal intubation, the number of intubation attempts, and the rate of successful endotracheal intubation on first attempt and success of endotracheal intubation within 120 seconds will be recorded. The subjective (rating 1 to 10) for ease of device use and laryngoscopic view judged by the percentage of glottic opening score (POGO) will be recorded. Comparison of these values between experienced and inexperienced users will be performed as well as comparison of CMAC, Glidescope, Miller blade, and Macintosh blade.

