**Identify the variables to be measured and how they will be statistically evaluated:**

Time to endotracheal intubation, the number of intubation attempts, and the rate of successful endotracheal intubation on first attempt and success of endotracheal intubation within 120 seconds will be recorded. The subjective (rating 1 to 10) for ease of device use and laryngoscopic view judged by the percentage of glottic opening score (POGO) will be recorded. Comparison of these values between experienced and inexperienced users will be performed as well as comparison of CMAC, Glidescope, Miller blade, and Macintosh blade. Pairwise comparisons among laryngoscopy methods will be performed using paired t-tests for continuous data and McNemar tests for categorical data. Repeated measures ANOVA will be used to assess the moderating effect of user experience on the difference in time to intubation between VL and DL.

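### Device order is not specified, randomised or recorded, so practice over the four intubations could pass for a difference between videolaryngoscopy and direct laryngoscopy

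*Combined protocol and SAP*

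**What the plan says.** The section outlining the major steps sets up a within-participant comparison: "Each participant will perform endotracheal intubation on the mannequin using both types of laryngoscope blades and both types of indirect laryngoscopes", four intubations per person. The power statement there is for a two-tailed paired t-test on 10 subjects, which "would have 80% power to detect a 15s difference in time to intubation between videolaryngoscopy and direct laryngoscopy". It then says that "the study will recruit 10-20 personnel from each of the following 4 groups".

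The section on variables begins its list with "Time to endotracheal intubation, the number of intubation attempts, and the rate of successful endotracheal intubation on first attempt" and adds success within 120 seconds, an ease rating and the POGO score. The number of attempts is an outcome; it does not say whether a device was used first or fourth. The analysis reads: "Pairwise comparisons among laryngoscopy methods will be performed using paired t-tests for continuous data and McNemar tests for categorical data". For experience, "Repeated measures ANOVA will be used to assess the moderating effect of user experience on the difference in time to intubation".

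Neither section, nor the objectives or the hypothesis, mentions device order, randomisation, counterbalancing, a practice run or an attempt-position term.

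**The concern.** Each participant repeats one task on one manikin four times, and some are trainees or medical students. Improvement within the session is plausible. The plan does not prescribe a common order, but nothing in it prevents one. With a common order, position in the sequence and device are the same variable.

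Three aims depend on within-participant differences:

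- **Time to intubation.** With the direct laryngoscopes early and the videolaryngoscopes late, practice creates or inflates a videolaryngoscope advantage. The reverse order masks one.
- **Experience.** The objectives state: "We hypothesize that this difference will be greatest for users with the least experience in DL". If novices gain more per attempt than experts, placing direct laryngoscopy early produces this same pattern with no true interaction.
- **Success.** The stated hypothesis is that inexperienced users "will achieve higher overall success rates using videolaryngoscopes than using a direct laryngoscope". The McNemar comparisons share the weakness, though its size was not calculated for them.

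**Working it through.** **Inputs from the plan** (section outlining the major steps): SD 15 s, given for videolaryngoscopy (VL); r = 0.5; target difference 15 s; two-sided 5%; n = 10 to 20 per group.

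**Assumptions:** the same SD for direct laryngoscopy (DL); one order for everyone; one try per device; a gain of L = 1, 2, 3 or 5 s per successive intubation. L is not in the documents, so the results are illustrations.

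**1. The plan's own figure.** SD of a paired difference = √(15² + 15² − 2 × 0.5 × 15 × 15) = 15 s. The noncentral t with 9 df and noncentrality (15/15) × √10 gives power of 80.3%. The plan's 80% is reproduced and is not in dispute.

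**2. Can device and position be separated?** Take 12 illustrative participants and a model with participant (12), device (3) and position (3) effects, 18 columns in all. Under one common order the rank is 15, so all three position effects are aliased with the device effects. Under a balanced Williams square the rank is 18 and both can be estimated.

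**3. Bias in the average contrast.** The SD of mean DL minus mean VL is √(15² × 0.5) = 10.6 s. With a linear gain, the bias is L times the difference in mean position:

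- blocked (DL, DL, VL, VL): 3.5 − 1.5 = 2, so 2L
- alternating (DL, VL, DL, VL): 3 − 2 = 1, so L
- symmetric (DL, VL, VL, DL): 2.5 − 2.5 = 0

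**4. False positives with no true difference** (exact noncentral t, average contrast):

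| Order and practice curve | n | L=1 | L=2 | L=3 | L=5 |
|---|---|---|---|---|---|
| Blocked, linear | 10 | 8% | 19% | 36% | 76% |
| Blocked, linear | 20 | 13% | 36% | 67% | 98% |
| Alternating, linear | 10 | 6% | 8% | 13% | 27% |
| Alternating, linear | 20 | 7% | 13% | 22% | 52% |
| Blocked, gain halves each time (bias 1.125L) | 10 | 6% | 9% | 15% | 32% |
| Alternating, gain halves (bias 0.625L) | 10 | 5% | 6% | 8% | 13% |
| DL first, all gain after the first intubation (bias 0.5L) | 10 | 5% | 6% | 7% | 10% |

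A larger sample raises the error, because the bias stays and the standard error shrinks. The symmetric order stays at 5% under a linear gain. For a single VL–DL pair at L = 5 and n = 10, the rate is 16, 47 or 80% when the devices are 1, 2 or 3 positions apart.

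**5. The reverse order.** With VL first, a true 15 s benefit and n = 10, the expected difference is 15 minus the bias. For L = 1, 2, 3, 5 s, power for the average falls from 98% to 93, 83, 67, 27% (blocked) or 96, 93, 89, 76% (alternating).

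**6. False experience interaction.** A two-sample t-test on within-person averages, 10 per group, has bias 2 × (difference in gain) if blocked and 1 × if alternating:

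| Gain per attempt, novice v experienced | Blocked | Alternating |
|---|---|---|
| 5 v 0 s | 51% | 17% |
| 5 v 1 s | 36% | 13% |
| 3 v 1 s | 13% | 7% |
| 2 v 1 s | 7% | 5.5% |

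**7. The remedy, by simulation.** Orders were randomised for each participant and the planned paired t-tests were used, with L = 1 to 5 s and n = 10 or 20. Mean bias is below 0.03 s, and false positives are 4.9–5.2% for the average and for one pair. For the interaction, at the gains in step 6, they are 4.7–5.5%. At L = 5 and n = 10, power for 15 s is 92% without and 98% with a position term for the average, and 67% against about 80% for one pair.

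**The case against.** The strongest reply is that this is an omission in a short form, not a stated error. Harm needs two things that the plan does not assert: one order for everyone and a material practice gain. The most striking rates use the largest assumed gain. At 5 s per step the total over the session is 3 × 5 = 15 s, as large as the whole target effect. The blocked order is the least favourable of the three examined, and the 51% interaction figure also supposes that experienced users gain nothing. Under milder curves the error stays near 5%. All of this stands. It limits the claim to a bias that could be serious; it does not show that one will occur.

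A symmetric order also cancels a practice gain in the average, even when everyone follows it. That is true only for a linear gain. If the gain halves each time, the mean changes from the first intubation are 0.875L for DL and 1.25L for VL, leaving a bias of 0.375L. Single-device pairs remain biased in any common order.

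Two smaller points are fair. All the figures concern time, so the effect on success rates is argued by the same logic and not calculated. The position term serves precision only, since randomised order alone gives valid tests.

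Staff may intend to vary the order anyway. If so, one sentence settles the matter. Without it nothing requires variation, and an order that varies but is not recorded cannot be adjusted for.

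**Conclusion.** The concern holds. The plan leaves device order open, does not record it and does not model it. If a single order were used, practice would be aliased with device, and the data could not separate them without outside assumptions about the learning curve. The size cannot be fixed from the documents. Over the linear gains of 1 to 5 s examined, false positives for the average contrast at n = 10 run from 6 to 27% with alternating order and from 8 to 76% with blocked order. They are close to 5% when the gain is small or ends early. These figures assume normal times, equal SDs, r = 0.5 and one try per device. This should be fixed before the first participant, because a common order cannot be repaired afterwards.

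**What to change.** **Needed.** In the section outlining the major steps, add: *The order of the four devices will be randomised for each participant within each user group, and the position (1 to 4) of each device will be recorded.* Device position is clearer than attempt number, because several tries with one device are already counted as an outcome. If order is already meant to vary, say how.

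**Worth adding, for precision.** In the section on variables, include device position as a fixed effect in the repeated-measures model and take the VL–DL contrast from that model.

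**Optional.** Use a 4 × 4 Williams square, with near-balance acceptable at any group size from 10 to 20, and a position-by-group term.

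**Cost.** A sequence list for 40 to 80 people (4 groups of 10 to 20), one recorded field and two sentences. With 40 participants and 160 intubations, residual df after participant, device and device-by-group effects are 160 − 40 − 3 − 9 = 108. The position term leaves 105, and the optional position-by-group term leaves 96. No extra participants, intubations or equipment are needed.

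Randomising order does not remove device-specific carry-over, such as a view learned with one device helping with the next. That limitation should be stated.

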**Identify the variables to be measured and how they will be statistically evaluated:**

Time to endotracheal intubation, the number of intubation attempts, and the rate of successful endotracheal intubation on first attempt and success of endotracheal intubation within 120 seconds will be recorded. The subjective (rating 1 to 10) for ease of device use and laryngoscopic view judged by the percentage of glottic opening score (POGO) will be recorded. Comparison of these values between experienced and inexperienced users will be performed as well as comparison of CMAC, Glidescope, Miller blade, and Macintosh blade. Pairwise comparisons among laryngoscopy methods will be performed using paired t-tests for continuous data and McNemar tests for categorical data. Repeated measures ANOVA will be used to assess the moderating effect of user experience on the difference in time to intubation between VL and DL.

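### The moderation hypothesis is about experience in direct laryngoscopy, but no listed variable measures it and the role groups cannot isolate the least experienced users; recording prior intubation counts is a cheap improvement

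*Combined protocol and SAP*

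**What the plan says.** The objectives section gives the study goal as testing whether time to intubation is shorter with VL than with DL, and adds: "We hypothesize that this difference will be greatest for users with the least experience in DL". The section on variables and their evaluation assigns the analysis: "Repeated measures ANOVA will be used to assess the moderating effect of user experience" on the VL–DL difference in time. It also announces a two-level comparison: "Comparison of these values between experienced and inexperienced users will be performed".

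The listed variables are time to intubation, number of attempts, first-attempt success, success within 120 seconds, ease rating and POGO score. Prior experience is not among them, and no section says who counts as experienced.

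The only grouping is by role, in the section on major steps and methodologies: "Therefore, the study will recruit 10-20 personnel from each of the following 4 groups". The third group is "Trainees (SRNAs, residents, and fellows, and medical students". Each participant uses two direct blades and two videolaryngoscopes ("total of 4 intubation attempts each").

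Two other sections describe inexperience differently. The significance section has "The inexperienced users in intubation of children will use VLs on a pediatric manikin". The hypothesis on success rates concerns "Performers who are inexperienced about direct laryngoscopy and VL".

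**The concern.** A moderation test needs a moderator that is measured or can be derived. The hypothesis names one, experience in DL, but nothing listed captures it. The text does not rule out that it would be collected, but it does not provide for it either. If it is not asked, it cannot be supplied at analysis.

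The natural substitute is the four role groups. They carry no stated mapping to experience, and the trainee group spans medical students to fellows. All of them receive the same factor level, although they probably differ in DL experience more than any other group does. The users to whom the hypothesis refers are then partly hidden inside a mixed group.

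Two results are at stake: the moderation test, and the comparisons of experienced with inexperienced users, including the success-rate hypothesis, whose population is undefined.

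**Working it through.** **1. The plan's own figure.** Inputs from the section on major steps: n = 10, difference 15 s, SD 15 s, r = 0.5, two-tailed 5%. The SD is stated for VL; the same SD is assumed for DL.

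SD of one DL-minus-VL difference = √(15² + 15² − 2 × 0.5 × 15 × 15) = 15.0 s. Noncentrality = (15/15) × √10 = 3.16 on 9 df, which gives power 80.3%. The stated 80% reproduces. It covers VL versus DL within one subgroup, not the moderation test.

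**2. SD when both devices of each type are averaged** (r = 0.5 for all pairs assumed). Variance of a mean of two = 225 × (1 + 0.5)/2 = 168.75. Variance of the difference = 2 × 168.75 − 2 × 0.5 × 225 = 112.5, so the SD is 10.6 s.

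**3. Power of the moderation test: illustration only.** Assumptions not in the documents: VL benefit 15 s in novices and 0 s in others; groups 1 and 2 experienced; group 4 all novices; a share s of group 3 novices. When s = 0.5 the four group means are 0, 0, 7.5 and 15 s. A split of groups 1–2 against 3–4 then estimates 15 × (0.5 + 1)/2 = 11.25 s instead of 15 s.

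The role analyses and the misclassified case were simulated (40,000 runs each, accurate to about half a percentage point). True experience with s = 0.5 compares 15 novices with 25 others: noncentrality = 15/(15 × √(1/15 + 1/25)) = 3.06 on 38 df, power 85%.

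Power (%), n = 10 per group, SD 15 s:

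| s | Four groups, 3 df | 1–2 v 3–4 | 1–3 v 4 | True experience | Experience, 10% misclassified |
|---|---|---|---|---|---|
| 0 | 57 | 29 | 76 | 76 | 50 |
| 0.5 | 49 | 60 | 56 | 85 | 62 |
| 0.8 | 60 | 78 | 44 | 87 | 65 |
| 1 | 71 | 87 | 36 | 87 | 66 |

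- **Averaged times (SD 10.6 s), n = 10:** four-group test 80–96%, true experience about 96–99%, 10% misclassified 75–89%.
- **SD 15 s, n = 20:** 85–97%, 97–99% and 80–92% respectively.
- **Averaged times, n = 20:** four-group test and true experience both 99% or more.

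When group 3 really is mixed (s = 0.5 or 0.8), experience with 10% misclassification still beats the four-group test. At s = 0 or 1, where group 3 is homogeneous, it does not. It does not reliably beat a two-group role split that happens to match the true mix: at s = 0.8 it has 65% against 78%.

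**4. Error rate with no moderation** (simulated, n = 10 or 20 per group). The four-group test alone holds 5%. If the analyst may pick the smaller p-value of the 1–2 v 3–4 split and the four-group test, the chance of p < 0.05 is 8%. For the two splits 1–2 v 3–4 and 1–3 v 4 it is 9%. Adding 1–2 v 4 and the four-group test to those two splits gives 11–12%.

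**The case against.** The strongest reply is that the plan already has a usable default. The sample-size text powers a given subgroup at 10 and from that recruits 10–20 in each of four groups. Read that way, the between-subject factor is role, with four levels and a valid 5% test. This largely stands. What it does not answer is that the hypothesis is about DL experience, that role does not measure it among trainees, and that four groups do not define the two-level comparison also planned.

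A reader might infer that the moderator is contradictory because inexperience is worded in several ways. The documents do not support that for the moderation test. The objectives name one construct, DL experience. The wording about DL and VL belongs to a different hypothesis, on success rates, and the wording about children is narrative.

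A reader might also infer that the test has an error rate of 8–12%. That is a worst case: it requires choosing the grouping by its p-value after seeing the data. Nothing in the plan says that this will happen, and some of the groupings are implausible (one classes medical students as experienced, another drops a recruited group).

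Finally, one could simply write down a mapping of roles to experience, with no recall error. That would settle the choice of analysis, but it would still leave students and fellows together.

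**Conclusion.** The point holds as a cheap improvement, not as a flaw that invalidates the study. The planned ANOVA, run on role groups, cannot isolate the users with the least DL experience, and no listed variable would allow it to. This follows from the text and needs no assumed figures.

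The cost in power is not fixed by the documents. Under the assumed effect, with 10 per group and single times, it is 49–71% for the four-group test against 76–87% by true experience. With averaged times and 20 per group it is negligible. These figures depend on the assumed 15 s effect in novices only, the assumed novice shares and the stated SD and correlation. They do not show that the fix will raise power: about 10% misclassification removes the advantage over a well-chosen two-group role split, and over the four-group test when trainees are in fact homogeneous. The dependable gain is a pre-specified moderator that matches the stated hypothesis.

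The within-person comparison of VL with DL and its 80% power are unaffected.

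**What to change.** 1. Before the first attempt, record each participant's number of prior DL and prior VL intubations in all patients, with children counted separately if wanted. Asking beforehand keeps performance from colouring the answer.
2. Pre-specify the method-by-experience test as one degree of freedom: regress each participant's mean DL minus mean VL time on the prior DL count, for example as log(count + 1). The documents give no distribution of counts, so the power of this form has not been calculated.
3. Define inexperienced users for the success-rate hypothesis from the same DL and VL counts, with a cut-off fixed before data collection.
4. Keep the four role groups as recruitment strata and the four-group (3 df) test as the pre-specified secondary analysis.

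The cost is two questions per participant (more if children are counted separately) and a few sentences of analysis text. No extra participants or staff are needed. The downside is recall error in self-reported counts. Retaining the role test limits the consequence, because role is known without error.

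### The experience-moderation test has no safeguard against unequal variances, so with unequal group sizes its type I error can drift from 5% (about 2% to 11% in a simple assumed example)

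*Combined protocol and SAP*

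**What the plan says.** The objectives statement sets out to test whether intubation is quicker with VL than with DL, and adds: "We hypothesize that this difference will be greatest for users with the least experience in DL". The section on variables and statistical evaluation gives the methods. Laryngoscopy methods are compared pairwise by "paired t-tests for continuous data", and repeated measures ANOVA is used for the "moderating effect of user experience on the difference in time to intubation between VL and DL". That section names no transformation, no method for unequal variances and no coding of experience.

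The methodology section gives the sample size: "the study will recruit 10-20 personnel from each of the following 4 groups". The groups are faculty pediatric anesthesiologists, CRNAs, trainees (including medical students), and APNs/nurses. The effect size is in seconds: the study is sized "to detect a 15s difference in time to intubation between videolaryngoscopy and direct laryngoscopy". The only spread given is 45 ± 15 s with VL. There is no SD for DL and no mean or SD for any single group.

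**The concern.** With one VL and one DL value per person, the group-by-method interaction in a repeated measures ANOVA is a one-way ANOVA on the within-person differences. Its F test uses one error variance for all groups. If spread differs between groups and sizes are equal, the test is fairly robust. If sizes differ as well, the pooled variance is dominated by the larger groups. The test then rejects too often when the small groups are the variable ones, and too rarely when the large groups are.

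Both conditions are plausible here. The groups are picked to span a wide range of skill, and slower users usually vary more in seconds. Recruitment of 10 to 20 per group allows a two-fold size difference. Moderation by experience is a stated hypothesis, so the reader needs to know that a p-value below 0.05 carries a 5% error rate. Under the plan as written, that rate depends on which group happens to recruit well.

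**Working it through.** **The plan's own figure.** Inputs from the methodology section: "a two-tailed paired t-test on a sample of 10 subjects would have 80% power", "at a 95% confidence level", a 15 s difference, SD 15 s, and "low within-subject correlation ( $r=0.5$ ) between times to intubation". Taking the DL SD equal to the VL SD:

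- SD of the difference = √(15² + 15² − 2 × 0.5 × 15 × 15) = √225 = 15 s.
- Noncentrality = √10 × 15/15 = 3.16, with 9 degrees of freedom.
- Power = 80.3%, which reproduces the stated 80%.

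The within-group sample size is therefore sound on its own terms. It does not address the moderation test.

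**Assumptions for the moderation test (not in the documents).** Times are log-normal. The coefficient of variation is 1/3, carried over from 45 ± 15. The correlation is 0.5. Each person gives one VL and one DL time. The slow group averages 60 s and the fast group 30 s with both methods, so there is no VL-DL effect and no moderation. The SD of a single time is then 20 s in the slow group and 10 s in the fast group. With r = 0.5, the SD of the difference is also 20 s and 10 s (variances 400 and 100).

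**Why the pooled test drifts.** Compare the true variance of the contrast between groups with the variance the pooled test uses on average.

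- 10 slow v 20 fast. True: 400/10 + 100/20 = 45. Pooled: [(9 × 400 + 19 × 100)/28] × (1/10 + 1/20) = 196.4 × 0.15 = 29.5. The standard error is understated: √(29.5/45) = 0.81.
- 15 v 15. True: 400/15 + 100/15 = 33.3. Pooled: 250 × 2/15 = 33.3. Ratio 1.
- 20 slow v 10 fast. True: 400/20 + 100/10 = 30. Pooled: [(19 × 400 + 9 × 100)/28] × 0.15 = 303.6 × 0.15 = 45.5. The standard error is overstated: √(45.5/30) = 1.23.

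**Simulated rejection rates at nominal 5%** (40,000 trials per setting):

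| Slow v fast | Pooled | Welch |
|---|---|---|
| 10 v 20 | about 11% | about 5% |
| 15 v 15 | about 5% | about 5% |
| 20 v 10 | about 2% | about 5% |

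**Sensitivity to the assumptions.** In the adverse 10 v 20 split, moving the fast group to 40, 45 or 50 s lowers the pooled rate to about 8.3%, 7.3% and 6.6%. A four-group version (equal true differences) gave the following for the classical F test:

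- Sizes 20, 20, 10, 10 with SDs 10, 10, 20, 20: 13.2%.
- The same sizes with SDs 10, 10, 30, 30: 17.7%.
- Sizes 10, 10, 20, 20 with SDs 10, 10, 20, 20: 2.8%.
- Equal sizes with unequal SDs: 5.7% to 7.5%.
- Equal SDs: 5%.

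Over the sizes the plan allows and the SDs tried, the range was about 2% to 18%. Welch stayed close to 5% throughout.

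**The case against.** **The size is conditional.** The plan does not schedule unequal groups, does not say which group would be small, and gives no group-specific SD. Reaching 11% in the two-group example takes a 2:1 split, a doubled SD, and the slow group being the small one. With equal sizes the pooled test is close to nominal, and with the reverse imbalance it is conservative. This stands, so 11% cannot be quoted as the plan's error rate. The lack of control remains, because the rate depends on recruitment.

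**Pooling is inferred.** The plan says only repeated measures ANOVA. Pooling is the standard form, and nothing in the text departs from it, but one sentence from the authors could settle the matter.

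**The simulation is simplified.** Each participant uses two devices of each type, and the plan does not say how they are combined. The exact figures would change with that choice. The mechanism would not.

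**A stronger reading about scale.** A reader might infer that analysing seconds is itself an error: if VL saves the same 25% for everyone, slower users save more seconds and moderation is declared. With novices at 45/60 s (VL/DL), that happens in 19% and 36% of simulated trials (10 v 10 and 20 v 20) against experts at 22.5/30 s, and in 35% and 64% against experts at 15/20 s. On the log scale the rate is about 5%. The documents do not support calling these false positives. The mean savings in seconds really do differ (15 s v 7.5 s or 5 s), and the objectives, the sample size and the analysis section all frame the effect as a difference in time. Log time also has the mirror property: an identical 15 s saving (45/60 v 15/30 s) is flagged as moderation on the log scale in 76% to 97% of trials, against 5% to 6% in seconds. The choice of scale changes the question asked, and the protocol's question is absolute.

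**Conclusion.** The point holds as a matter of unequal variances. The planned moderation test has no protection when group sizes and spreads both differ, and the design makes both plausible. In the two-group example its type I error is about 11%, 5% or 2%, depending on whether the slower group is half the size, equal in size or twice the size. Welch gives about 5% in each case. These figures rest on the assumed 60 s and 30 s means, coefficient of variation 1/3, log-normal shape, correlation 0.5 and one value per method per person.

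The point does not extend to requiring log time as the primary scale, or to accepting moderation only if it also holds as a ratio. What does carry over from the scale question is interpretation. A larger saving in seconds among novices may or may not be a larger percentage saving, and the plan should let the reader see which.

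**What to change.** Replace the moderation sentence in the analysis section with wording to this effect: moderation by experience will be tested on each participant's DL-VL difference in seconds, using a method with group-specific variances (Welch ANOVA, or a mixed model with heterogeneous group variances); VL/DL ratios of geometric means will be reported by group as a sensitivity analysis. The same sentence should say how the two devices of each type are combined into one difference per person, and how experience is coded.

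The cost is a slight loss of degrees of freedom and one extra analysis. No additional participants or measurements are needed. Aiming for similar group sizes would also help, but does not replace the change in method.
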